Subjects who successfully complete all study doses in Sentinel Cohort 1 and show a reduction in plasma HIV RNA $> 0.5 \log_{10}$ from their pre-GS-9131 baseline following functional monotherapy will discontinue their current failing regimen and start an optimized regimen consisting of GS-9131 (60 mg) + BIC + DRV + RTV for at least 24 weeks.

GS-9131(up to 180 mg) + BIC (75 mg) + TAF (25 mg) (Sentinel Cohort 2 and Randomized Cohort)

Subjects who successfully complete all study doses in Sentinel Cohort 2 and Randomized Cohort (A-C), and show a reduction in plasma HIV RNA $> 0.5 \log_{10}$ from their pre-GS-9131 baseline during functional monotherapy will discontinue their current failing regimen and start an optimized regimen consisting of GS-9131 + BIC + TAF for at least 24 weeks. All Subjects randomized to the placebo arm (Cohort D) will discontinue their current failing regimen and start a regimen consisting of GS-9131(180 mg) + BIC + TAF for at least 24 weeks.

CCI

An Independent Data Monitoring Committee (IDMC) will review the progress, efficacy, and safety data while the study is ongoing. The committee will convene after all subjects in the randomized cohort have completed Part 1 and after approximately 50% of subjects in Part 2 have completed Week 12 of Part 2 of the study.

Number of Subjects
Planned:

Approximately 68 female subjects will be enrolled in this study. Replacement subjects may be enrolled for subjects who do not complete all procedures in the functional monotherapy treatment for reasons other than discontinuation due to treatment related adverse events (AEs).

Target Population:	HIV-1 infected adult females ≥ 18 years of age failing a 2 nucleoside reverse transcriptase inhibitor (NRTI) + non-nucleoside reverse transcriptase inhibitor (NNRTI) containing treatment regimen with plasma HIV-1 RNA level ≥ 500 copies/mL, evidence of K65R or 3 or more thymidine analog mutations (TAMs) or Q151M, and at least one documented primary resistance associated mutation to NNRTIs.
Duration of Treatment:	Part 1 Sentinel Cohort 1: 10 days. Part 1 Sentinel Cohort 2 and Randomized Cohort : 14 days each Part 2: At least 24 weeks

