All subjects will be required to visit the clinic on Day 1, and Weeks 1, 2, 4, 8, 12, 18, and 24. At each visit, AEs, concomitant medications, drug accountability, hematology, chemistry, HIV-1 RNA, CD4 cell count, vital signs, and estimated GFR will be evaluated. A fasting metabolic profile will be performed on Day 1, Week 12 and 24 visits. A complete physical examination will be done at Day 1, Week 12 and 24 visits. A symptom directed physical examination will be done at all other visits. Urinalysis will be performed at Day 1, and Week 4, 12, and 24 visits. Urine pregnancy test (females of childbearing potential only) will be done on Day 1, and Weeks 4, 8, 12, 18, and 24; positive urine pregnancy test will be confirmed with a serum pregnancy test.

CCI [REDACTED]

CCI [REDACTED]

CCI [REDACTED]

Protocol-Specific Stopping Rules

By Subject: Study drug dosing for a subject will be discontinued if that subject experiences a Grade 3 or Grade 4 treatment-emergent adverse event (AE) or confirmed laboratory abnormality judged by the study investigator to be possibly related to study drug, or any serious adverse event (SAE) considered to be possibly related to study drug.

By Sentinel Cohort: Study drug dosing for the Sentinel Cohorts will be discontinued if any of the following criteria is met:

- 2 or more subjects experiencing Grade 3 or Grade 4 treatment-emergent AEs judged by the study investigator to be possibly related to study drug, or
- 2 or more subjects experiencing confirmed Grade 3 or Grade 4 laboratory abnormalities, or
- 2 or more subjects experiencing any SAE that is considered to be possibly related to study drug.

For the Randomized Cohort and Part 2: If 2 or more subjects in the Randomized Cohort who are subsequently assigned to treatment cohorts in Part 2 experience a Grade 3 or 4 treatment-emergent AE leading to study drug discontinuation or an SAE judged by the study investigator to be possibly related to study drug, the IDMC will be convened to review all preliminary safety data generated in subjects dosed to date.

Subjects will be followed as clinically indicated until the treatment-emergent AE or laboratory abnormality returns to baseline or is otherwise explained, whichever occurs first. Grade 3 and 4 laboratory abnormalities that are not confirmed by repeat testing will be managed according to the clinic's practice; a decision to reinitiate dosing may be made by Gilead in consultation with the investigator and after a safety review.

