1.9. Risk/Benefit Assessment for the Study

All patients with HIV-1 infection, including those with drug resistant viruses, benefit from receiving effective ART. The risks in the study patient population who are failing their current ARV regimen are considered to be low. Important risks will be appropriately managed by study inclusion/exclusion criteria, as well as close monitoring during the study.

All subjects will be monitored daily during the functional monotherapy period and at frequent intervals in Part 2 of the study. Monitoring will include clinical evaluation, safety laboratory tests, and HIV-1 RNA viral load. In addition, stopping criteria will be implemented on an individual and cohort basis and the study will be monitored by an independent data safety monitoring board as well as local ethics committees. Important risks will be appropriately managed by study inclusion/exclusion criteria, as well as close monitoring, including clinical evaluation, safety laboratory assessment, individual and by-cohort stopping rules, and HIV-1 RNA viral load monitoring during the study.

If a median of > 0.5 log decrease in HIV-1 RNA is observed following administration of GS-9131 180 mg in the second Sentinel Cohort, GS-9131 doses ≤ 180 mg may be evaluated in the Randomized Cohort.

The only significant effect identified in chronic animal studies with BIC was hepatobiliary toxicity in monkeys following 39 weeks of administration at a dose (1000 mg/kg/day) which produced plasma exposures to BIC that were 16-fold higher than those observed in patients at a 50 mg BIC dose. The effects were partially reversible after a 4-week period of non-exposure (recovery). No toxicity was observed at the mid-dose of BIC 200 mg/kg/day, which provided a margin of exposure 7-fold greater than the projected clinical exposure. Potential hepatobiliary toxicity is appropriately managed by study inclusion/exclusion criteria, close clinical and laboratory monitoring, as well as specific toxicity management guidance to investigators. As of 06 August 2018, 2740 subjects have been exposed to B/F/TAF in clinical trials with no evidence of hepatotoxicities. (Refer to BIC & TAF IB).

Consistent with other members of the INSTI class, BIC has been well-tolerated in clinical studies to date.

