3.3. Study Treatments

Subjects who provide written consent and meet all eligibility criteria will be allocated to one of the following treatment groups as follows:

Part 1: GS-9131 Functional Monotherapy

Part 1 consists of 3 cohorts:

Sentinel Cohort 1:

Approximately 10 TE viremic HIV-1 subjects will be enrolled to receive open-label GS-9131 60 mg in addition to their current failing ARV regimen.

Sentinel Cohort 2:

Up to 10 TE viremic HIV-1 subjects will be enrolled to receive open-label GS-9131 180 mg in addition to their current failing ARV regimen.

Randomized Cohort:

Up to 48 subjects failing their current ARV regimen will be randomized to GS-9131 (up to 180 mg) or PTM. These drugs will be added to their failing regimen for 14 days described below. Doses and number of cohorts will be determined by data from Sentinel Cohort 2:

- Treatment Arms A-C: GS-9131 up to 180 mg once daily + current failing ART regimen (n=12 per cohort)
- Treatment Arm D: PTM GS-9131 + current failing ART regimen (n=12)

Randomization will be stratified by HIV-1 RNA level ($\leq 100,000$ copies/mL and $> 100,000$ copies/mL) at screening.

Subjects enrolled in Part 1 who do not successfully complete the study drug doses in Part 1 will not continue onto Part 2 of the study.

Subjects enrolled in Part 1 who do not show a reduction in HIV RNA $> 0.5 \log_{10}$ from baseline to Part 2 Day 1 will have an Early Study Drug Discontinuation (ESDD) visit within 72 hours of laboratory results being available. They will have study medications discontinued and will not continue to Part 2.

Part 2 (Sentinel Cohort 1): GS-9131 + BIC + DRV+ RTV Regimen

In Part 2, subjects in Sentinel Cohort 1 will start a regimen consisting of GS-9131 (60 mg) + BIC (30 mg) + DRV+RTV (800 mg/100 mg) for 24 weeks. CCI

Part 2: GS-9131 + BIC + TAF Regimen (Subjects in Sentinel Cohort 2 and Randomized Cohorts)

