All subjects who successfully complete all study drug doses in Sentinel Cohort 2 and the Randomized Cohorts will discontinue study drug from Part 1 on Day 15. To continue to Part 2, subjects must have a $> 0.5 \log_{10}$ decline in plasma HIV-1 RNA from their pre-GS-9131 baseline in the 14 days of functional monotherapy. Since this result will not be immediately available at the completion of Part 1, all subjects completing Part 1 will continue on their failing regimen until results are available. Results will be available no later than 9 days after completion of Part 1. Subjects who meet criteria will proceed to Day 1 of Part 2. Any subjects in the Sentinel Cohort, and Treatment Arms A, B and C who do not meet the criterion for $> 0.5 \log_{10}$ decline in plasma HIV-1 RNA from their pre-GS-9131 baseline will not continue to Part 2. All subjects in Treatment Arm D will be eligible to continue to Part 2. In Part 2, subjects from the Sentinel Cohort 2 and the Randomized Cohort will start a regimen consisting of GS-9131 (up to 180 mg) + BIC (75 mg) + TAF (25 mg) as described below.

- Treatment Arms A-C: GS-9131 (up to 180 mg)+ BIC + TAF
- Sentinel Cohort 2 and Treatment Arm D: GS-9131 180 mg + BIC + TAF

At Week 8, subjects who have plasma HIV-1 RNA < 200 copies/mL or who have an HIV-1 RNA ≥ 200 copies/mL and a reduction in HIV-1 RNA $> 1 \log_{10}$ from baseline at any study visit will continue study medications.

Subjects who have a confirmed sub-optimal virologic response at Week 8 defined as plasma HIV-1 RNA ≥ 200 copies/mL and reduction in HIV-1 RNA $\leq 1 \log_{10}$ from baseline at all study visits up to Week 12 may be discontinued from the study and further optimization of their ARV regimen if feasible will be done by the Investigator. Subjects meeting criteria for sub-optimal virologic response as further defined in Section 6.10.1 will be contacted for an ESDD visit and discontinued from the study within 72 hours of results being available.

Subjects with protocol-defined virologic failure and evidence of treatment emergent resistance to any component of their regimen at any time will be discontinued from the study drug and treated with an ARV regimen chosen by the Investigator. For additional information, please reference ESDD (Section 6.4.1).

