3.4. Duration of Treatment

[figure not shown]
The duration of the Sentinel Cohort 1 in Part 1 of the study is 10 days. Subjects who successfully complete the functional monotherapy, defined as a $> 0.5 \log_{10}$ reduction in plasma HIV-1 RNA from baseline, will be administered GS-9131 (60 mg) + BIC (30mg)+ DRV (800 mg) +RTV (100mg) through Week 24. **CCI**

The duration of Sentinel Cohort 2 and Randomized Cohorts in Part 1 of the study is 15 days each. Subjects who successfully complete the 14 day functional monotherapy, defined as a $> 0.5 \log_{10}$ reduction in plasma HIV-1 RNA from baseline or who are from the PTM arm, will be administered GS-9131 + BIC (75 mg) + TAF (25 mg) through Week 24. Doses of GS-9131 for subjects in the Sentinel Cohort 2 and Placebo cohort will be 180 mg; doses of GS-9131 and PTM for subjects in the Randomized Cohorts Treatment Arms A-C will correspond to the respective dose selected for cohorts (A-C). All subjects will continue a regimen of GS-9131 + BIC (75 mg) + TAF (25 mg) at the assigned GS-9131 dose until determination of the optimal GS-9131 dose following Part 1 data review of the Randomized Cohort. **CCI**

[figure not shown]
Figure 2. Study Schema – Cohort 1

- a Randomization and dosing into the Randomized Cohort of Part 1 will begin after the Day 10 safety and efficacy data from the 10 subjects in the Sentinel Cohort are reviewed.
- b Subjects on GS-9131 (including all subjects in the Sentinel Cohort and those on Treatment Arm A, B, and C of the Randomized Cohort) who have a $\leq 0.5 \log_{10}$ decline in HIV-1 RNA will be discontinued from the study and will not be eligible to continue into Part 2 of the study. The Sponsor will notify the site regarding subject enrollment criteria for Part 2 prior to the visit.”
- c Subjects who complete Day 10 of Part 1 (from either the Sentinel Cohort or Treatment Arm D of the Randomized Cohort) will discontinue their GS-9131 or PTM but remain on their failing ARV regimen until the site is notified of the subject’s eligibility to proceed to Part 2.

Figure 3. Study Schema – Cohort 2

- a. Randomization and dosing into the Randomized Cohort of Part 1 will begin after the Day 15 safety and efficacy data from the Sentinel Cohort is reviewed.

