6.5.1. Study Stopping Criteria

By Subject: Study drug dosing for a subject will be discontinued if that subject experiences a Grade 3 or Grade 4 treatment-emergent adverse event (AE) or confirmed laboratory abnormality judged by the study investigator to be possibly related to study drug, or any serious adverse event (SAE) considered to be possibly related to study drug.

By Sentinel Cohort: Study drug dosing during Part 1 for the Sentinel Cohorts will be discontinued if any of the following criteria is met:

- 2 or more subjects experiencing Grade 3 or Grade 4 treatment-emergent AEs judged by the study investigator to be possibly related to study drug, or
- 2 or more subjects experiencing confirmed Grade 3 or Grade 4 laboratory abnormalities, or
- 2 or more subjects experiencing any SAE that is considered to be possibly related to study drug.

For the Randomized Cohort and Part 2: If 2 or more subjects in Part 1 of the Randomized Cohort who are subsequently assigned to treatment cohorts in Part 2 experience a Grade 3 or 4 treatment emergent AE leading to study drug discontinuation or an SAE judged by the study investigator to be possibly related to study drug, the IDMC will be convened to review all preliminary safety data generated in subjects dosed to date.

Subjects will be followed as clinically indicated until the treatment-emergent AE or laboratory abnormality returns to baseline or is otherwise explained, whichever occurs first. Grade 3 and 4 laboratory abnormalities that are not confirmed by repeat testing will be managed according to the clinic's practice; a decision to reinitiate dosing may be made by Gilead in consultation with the investigator and after a safety review.

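### The placebo arm's Part 2 dose is fixed at 180 mg with no stated link to the review that sets the randomized doses, and the sentinel-cohort stop has two different scopes

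*Protocol*

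**What the plan says.** **Arm D in Part 2.** Section 3.3 lists "Sentinel Cohort 2 and Treatment Arm D: GS-9131 180 mg + BIC + TAF" directly beside "Treatment Arms A-C: GS-9131 (up to 180 mg)+ BIC + TAF". Section 3.4 repeats it: "Doses of GS-9131 for subjects in the Sentinel Cohort 2 and Placebo cohort will be 180 mg". The Synopsis has the placebo arm "start a regimen consisting of GS-9131(180 mg) + BIC + TAF for at least 24 weeks", and SAP Section 1.2 says the same.

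**The dose review.** The Synopsis (Study Design) and note e to Figure 3 have the Sentinel Cohort 2 review determine the dose for Arms A-C. The Synopsis names safety, activity and available PK as what is reviewed. Section 3.3 adds: "Doses and number of cohorts will be determined by data from Sentinel Cohort 2". Section 1.9 makes the Randomized Cohort depend on a median fall of more than 0.5 log at 180 mg, after which "GS-9131 doses ≤ 180 mg may be evaluated in the Randomized Cohort".

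**Sentinel Cohort 2 in Part 2.** Sections 3.3 and 3.4 and SAP Table 8-1 state 180 mg. Section 5.3 reaches the same dose by carrying the Part 1 dose forward. The Synopsis (Part 2 regimen heading and Test Product entry) gives only an upper limit of 180 mg.

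**The sentinel stop.** The Synopsis (Protocol-Specific Stopping Rules) reads "Study drug dosing for the Sentinel Cohorts will be discontinued if any of the following criteria is met". Section 6.5.1 reads "Study drug dosing during Part 1 for the Sentinel Cohorts will be discontinued if any of the following criteria is met". In both places the next paragraph covers the Randomized Cohort and Part 2, but its trigger counts only Randomized Cohort subjects and leads to an IDMC meeting.

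**The concern.** Section 1.8.1 says that no clinical safety data existed for 180 mg when the protocol was written. The Sentinel Cohort 2 review is therefore the first clinical look at that dose, and the plan lets its outcome determine what Arms A-C receive. It does not say that the same outcome reaches Arm D. If the review selected only doses below 180 mg, a literal reading would start GS-9131-naive placebo subjects on 180 mg, together with BIC and TAF, when no subject had been randomized to that dose.

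The stopping-rule wording raises a separate problem. If the sentinel criteria were met while some Sentinel Cohort 2 subjects were already in Part 2, a site following the Synopsis would stop their study drug under the cohort rule. A site following Section 6.5.1 would not.

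**Working it through.** This is a comparison of texts. No stated figure decides it, and it does not depend on the sample-size calculation.

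1. **Status of 180 mg.** The plan's projected exposures reproduce from the 60 mg means in Table 5: GS-9131, 3 × 599 = 1797; GS-9148, 3 × 955 = 2865 (hr*ng/mL), as in Section 1.8.1. Before Sentinel Cohort 2, support for 180 mg was projected and not observed in patients.

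2. **Scope of the review.** The Synopsis and Figure 3 note e name Arms A-C only. Section 3.3 refers to doses and number of cohorts in general, but in the context of Part 1 of the Randomized Cohort. None of these names Arm D's Part 2 dose.

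3. **Two possible outcomes.**
   - 180 mg is among the randomized doses: Arm D's fixed dose matches a randomized arm, and there is no gap.
   - Every randomized dose is below 180 mg: Arms A-C carry their lower doses forward under Section 5.3. Arm D has no active Part 1 dose to carry forward, so the fixed 180 mg text governs. No visible passage addresses this case.

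4. **Whether later wording closes the gap.** Section 3.4 and Figure 3 note e keep subjects on the assigned dose until an optimal dose is determined. That depends on the Randomized Cohort's Part 1 review, a different and later one. Section 6.3.2 allows no more than 9 days between Part 1 and Part 2, whereas the Part 1 analysis in Section 8.11 waits for all subjects. If the dose decision follows that analysis (an assumption), subjects randomized early to Arm D would already be in Part 2. Redacted text follows the sentence in Section 3.4, so a linking rule could exist that cannot be seen.

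5. **Sentinel Cohort 2.** These subjects enter Part 2 only after 14 days on 180 mg and a fall of more than 0.5 log10. With a wait of at most 9 days, some could start Part 2 before the cohort review is complete. What remains is the difference between the Synopsis (an upper limit) and Sections 3.3, 3.4, 5.3 and SAP Table 8-1 (180 mg), with no statement of what follows if the review limits the dose.

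6. **Sentinel stop, for a Sentinel Cohort 2 subject in Part 2.**

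| Text | Cohort stop applies? | Counted toward the IDMC trigger? |
|---|---|---|
| Synopsis | Yes, no limit stated | No, Randomized Cohort only |
| Section 6.5.1 | No, Part 1 only | No, Randomized Cohort only |

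7. **Reach.** Dose point: at most 12 (Arm D, n = 12, those completing Part 1). Stopping-rule point: at most 10 (Sentinel Cohort 2, up to 10 enrolled, responders only).

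**The case against.** The strongest reply is that an upper limit of 180 mg for Arms A-C and 180 mg for Arm D are logically compatible, and that the choice of dose belongs to the sponsor. That stands: the point is the missing statement for one outcome of the review, not the dose itself.

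The triggering case is also narrow. The Randomized Cohort proceeds only if 180 mg shows a median fall above 0.5 log, and the permitted doses include 180 mg. Section 1.8.1 gives exposure-response as the purpose of the dose range, so lower randomized doses need not mean that the review found a safety problem. By-subject stopping, toxicity management and IDMC review continue to apply. All of this stands and limits the weight of the point.

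On the stop, the separate paragraph for the Randomized Cohort and Part 2 supports reading the sentinel rule as Part 1 only. Its criteria, however, do not count sentinel subjects, so it does not settle the matter.

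A reader might infer that 12 + 10 = 22 of 10 + 48 = 58 subjects (37.9%) are committed to 180 mg for 24 × 7 = 168 days, 12 times the 14 days reviewed. The documents do not support that as a fixed figure. Sentinel Cohort 2 non-responders do not enter Part 2, and its responders already know the dose. The Synopsis and the design text in SAP Section 1.2 do not fix that cohort's dose. Section 3.4 allows a later dose change. The 12-fold ratio is not specific to Arm D either, because Arms A-C also move from 14 days to 24 weeks.

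**Conclusion.** The point holds in a limited form. Arm D's Part 2 dose is fixed at 180 mg, the Sentinel Cohort 2 review sets doses for Arms A-C only and may set them lower, and no visible text says what happens to Arm D in that event. The reach is at most 12 GS-9131-naive subjects. This assumes that the review selects only doses below 180 mg and that the redacted text contains no linking rule. For Sentinel Cohort 2 the dose point is a weaker inconsistency of wording.

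The stop has two scopes, affecting at most 10 Sentinel Cohort 2 subjects. That is a planning maximum: SAP Section 2.4 reports 4 subjects in Part 2 in all.

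A reader might also infer that a planned comparison is damaged if 180 mg is not a randomized arm. The documents do not support that, because the Part 2 efficacy analyses in Section 8.5.2 are descriptive and make no between-group test. SAP Sections 2.4 and 6 record that the study stopped early with no randomized-cohort efficacy data, so the Arm D gap bears on the plan as written and not on reported results.

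**What to change.** Two reconciliations of wording are needed.

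- **Part 2 dose.** Reconcile the fixed 180 mg statements for Arm D (Synopsis, Sections 3.3 and 3.4, SAP Section 1.2) with the dose-review statements (Synopsis Study Design, Sections 1.9 and 3.3, Figure 3 note e), so that the text covers the case where all randomized doses are below 180 mg. For Sentinel Cohort 2, make the Synopsis agree with Sections 3.3, 3.4 and 5.3 and SAP Table 8-1.
- **Sentinel stop.** Make the Synopsis and Section 6.5.1 agree on whether the rule covers sentinel subjects already in Part 2.

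The sponsor decides both the dose and the scope of the rule. The cost is protocol and SAP wording and, if an assignment changes, an IWRS setting. No extra subjects or procedures are needed. As the study has ended, the practical use is in the study record and in any later protocol that reuses this design.

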6.10. Virologic Failure

Virologic failure is defined as virologic rebound (Section 6.10.2) or as suboptimal virologic response in relation to pre-GS-9131 baseline plasma HIV-1 RNA levels at the time points described below.

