6.10.1. Suboptimal Virologic Response

[figure not shown]
Subjects who meet the criteria listed below will be considered to have suboptimal virologic response (Figure 4):

- A) Functional monotherapy Sentinel Cohort 1: Suboptimal virologic response for Sentinel Cohort 1 is defined as a reduction in plasma HIV RNA $\leq 0.5 \log_{10}$ from pre-GS-9131 baseline after 10 days of GS-9131 functional monotherapy. This is assessed at Day 11 in Sentinel Cohort 1. Subjects meeting criteria for suboptimal virologic response will be contacted for an ESDD visit and discontinued from the study within 72 hours of these results being available.

Functional monotherapy Sentinel Cohort 2 and Randomized Cohorts: Suboptimal virologic response is defined as a reduction in plasma HIV RNA $\leq 0.5 \log_{10}$ from pre-GS-9131 at Day 15 during GS-9131 functional monotherapy period (excludes placebo group). Subjects meeting criteria for suboptimal virologic response will be contacted for an ESDD visit and discontinued from the study within 72 hours of these results being available.

- B) All Subjects Part 2: Suboptimal virologic response is defined as plasma HIV-1 RNA ≥ 200 copies/mL AND reduction in HIV-1 RNA $\leq 1 \log_{10}$ from pre-GS-9131 baseline at the Week 8 visit with confirmation at the next scheduled or unscheduled visit. Subjects with suboptimal virologic response at Week 8 will have a repeat test of plasma HIV-1 RNA 1-3 weeks later. If the repeat test shows a suboptimal virologic response defined as plasma HIV-1 RNA ≥ 200 copies/mL AND reduction in HIV-1 RNA $\leq 1 \log_{10}$ from pre-GS-9131 baseline, an HIV-1 genotype/phenotype will be done. If no new resistance to study drugs is detected from the genotype or phenotype, the subject may remain on study drugs and a repeat test of HIV-1 RNA should be conducted (1 to 3 weeks after the last HIV-1 RNA test). Investigators should carefully evaluate the benefits and risks of remaining on study drug for each individual subject and document this assessment in the on-site medical record. If new resistance to study drugs is detected, subjects will discontinue study drugs. For subjects who are off study drug but remain on study, it will be the Investigator's discretion to optimize their regimen and manage virologic rebound.

Figure 4. Suboptimal Virologic Response Schema

- a If virologic rebound is not confirmed, the subject will remain on their current regimen.

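### Protocol 3.3 orders a Part 2 suboptimal responder out of the study within 72 hours, while 6.10.1 B lets her stay on drug or in follow-up and uses a different trigger

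*Protocol*

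**What the plan says.** Protocol 3.3 handles Week 8 of Part 2 in two paragraphs.

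- **Continue rule.** A subject below 200 copies/mL, or at 200 or more with a fall of over 1 log10 "from baseline at any study visit will continue study medications".
- **Permissive sentence.** A confirmed suboptimal responder, at 200 copies/mL or more with a fall of at most 1 log10 "from baseline at all study visits up to Week 12 may be discontinued from the study".
- **Mandatory sentence, directly after.** Anyone meeting the 6.10.1 criteria "will be contacted for an ESDD visit and discontinued from the study within 72 hours of results being available".
- **Next paragraph of 3.3.** A subject with virologic failure and emergent resistance "will be discontinued from the study drug and treated with an ARV regimen chosen by the Investigator". This stops the drug, not study participation.

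Protocol 6.10 makes the suboptimal responder a virologic failure: "Virologic failure is defined as virologic rebound (Section 6.10.2) or as suboptimal virologic response". Section 6.10.1 then has two parts.

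- **Part A (Part 1 monotherapy).** Subjects "will be contacted for an ESDD visit and discontinued from the study within 72 hours of these results being available".
- **Part B (Part 2).** The criterion is 200 copies/mL or more and a fall of at most 1 log10 from the pre-GS-9131 value "at the Week 8 visit with confirmation at the next scheduled or unscheduled visit". A retest follows after 1 to 3 weeks, then genotype/phenotype. Without new resistance, "the subject may remain on study drugs and a repeat test of HIV-1 RNA should be conducted". With new resistance she stops study drugs, and the text provides for subjects who have stopped drug but are still on study.

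Protocol 6.4.1 asks sites to try to keep subjects in follow-up after drug stops, and allows withdrawal if that is not possible or acceptable. Appendix 3 note h asks for scheduled visits through Week 24 after drug stops.

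**The concern.** The mandatory sentence in 3.3 and the Part 2 rule it cites cannot both be followed. Whether a viremic participant keeps study drug, stops drug and is followed, or leaves the trial depends on which section the site reads. Two sites could treat identical subjects in opposite ways, each in line with the protocol. Read literally, 3.3 also handles failure without resistance more severely (out of the study) than failure with resistance (off drug only).

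At stake are participant management and the scheduled follow-up to Week 24, including the Week 24 HIV-1 RNA value. This is not a question of analysis method.

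**Working it through.** The plan gives no figure to reproduce. The check sets the texts side by side and applies them to two assumed subjects.

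**Disposition.** The permissive sentence of 3.3 is compatible with 6.10.1 B, since both leave room for judgement. The mandatory sentence is not: 6.10.1 B has no step that ends study participation.

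**Trigger.** Section 3.3 asks for a fall of at most 1 log10 at all visits up to Week 12, and keeps the subject on drug after a larger fall at any visit. Section 6.10.1 B asks for Week 8 plus one confirmation. It measures from the pre-GS-9131 baseline; the Week 8 paragraphs of 3.3 say only baseline, and Section 3.1 also uses a separate Part 2 baseline.

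**Two assumed subjects**, both with a pre-GS-9131 value of 10,000 copies/mL (log10 = 4.00) and 2,000 copies/mL at Week 8 and retest (log10 = 3.30; fall 4.00 − 3.30 = 0.70).

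- Case A: Week 2 is 4,000 (log10 = 3.60; fall 0.40), with no visit showing a fall above 1 log10.
- Case B: Week 2 is 600 (log10 = 2.78; fall 4.00 − 2.78 = 1.22). The rise from nadir is 3.30 − 2.78 = 0.52, below 1 log10, and she was never below 50 copies/mL, so this is not rebound under 6.10.2.

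| Rule | Case A | Case B |
|---|---|---|
| 3.3 continue rule | not met | stays on study drug |
| 3.3 permissive sentence | may leave the study | not met on a literal reading |
| 3.3 mandatory sentence | must leave the study | must leave the study |
| 6.10.1 B | genotyped; may stay on drug if no new resistance | same as Case A |

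**Follow-up at stake.** Part 2 visits are Day 1 and Weeks 1, 2, 4, 8, 12, 18 and 24, which is 8.

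- Retest 1 to 3 weeks after Week 8 falls at Weeks 9 to 11. Removal then loses Weeks 12, 18 and 24 (3 of 8 visits) and 24 − 11 = 13 to 24 − 9 = 15 weeks.
- Confirmation at the Week 12 visit loses Weeks 18 and 24 (2 of 8 visits) and 24 − 12 = 12 weeks.
- Two visits remain: early study drug discontinuation (ESDD) and the 30-day follow-up (6.4.1, 6.4.2). Both include HIV-1 RNA and CD4 in Appendix 3. Taking the later retest, 3 days to the ESDD visit and the 30-day visit at the end of its 6-day window gives 11 × 7 + 3 + 30 + 6 = 116 days, or 116/7 = 16.6 weeks. These visits do not supply a Week 24 value.

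Laboratory turnaround is not given and is ignored.

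**The case against.** The strongest defence is that the conflict rests on one misplaced sentence. It defers to 6.10.1, where nearly the same 72-hour wording occurs only in part A, so a sensible reader would confine it to Part 1. The carry-over is likely. But the sentence stands in the Week 8 paragraph, cites 6.10.1 without limit, and 3.3 already has a separate 72-hour visit sentence for Part 1 non-responders. A likely cause does not tell a site which rule to follow. The instruction in 7.6 to take the more conservative criterion covers toxicity management, not virologic failure.

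A second defence is that the trigger wording in 3.3 can be read as Week 8 plus confirmation by Week 12, which is close to 6.10.1 B. That is possible, but it fits poorly with the continue rule, which looks at any visit. The trigger difference therefore holds on a literal reading only.

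A reader might also infer more than the documents support:

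- **That removal ends all follow-up.** It does not; the ESDD and 30-day visits remain, although 6.4.2 words the latter for subjects who decline to continue.
- **That 6.4.1 forbids removal.** It favours retention but allows withdrawal.
- **That the Week 24 missing=failure/excluded analyses in Protocol 8.5.2 are undermined.** SAP 6 only lists Part 2 efficacy, so the question does not arise.

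**Conclusion.** The inconsistency is real and should be corrected, but its effect in this stopped trial is minor. The mandatory 72-hour sentence in 3.3 contradicts both the sentence before it and 6.10.1 B. The difference in triggers is secondary and depends on the literal reading.

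The primary endpoint is a Part 1 measure and is unaffected, as is the Snapshot rule. It would be wrong to infer either that reported efficacy is biased or that no planned output could change. SAP 2.4 mostly confines Part 2 to listings, but SAP 4.1 tabulates completion of Part 2 study drug and of the study, with reasons, and those counts could depend on the rule applied. Part 2 has 4 subjects (SAP 2.4). The documents do not say that any met either trigger, and Protocol 1.2.3.3 reports that one Sentinel Cohort 1 subject who entered Part 2 was suppressed below 50 copies/mL.

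Cases A and B are illustrations; how often either would occur is not given and not assumed.

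**What to change.** In Protocol 3.3, replace the two Week 8 paragraphs with: *Suboptimal virologic response in Part 2 is defined and managed only as in Section 6.10.1 B. Subjects who stop study drug are asked to continue scheduled visits through Week 24 (Section 6.4.1).* This deletes the 72-hour sentence from 3.3; it stays in 6.10.1 A for Part 1. Keep the resistance paragraph that follows, which agrees with 6.10.1 B.

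In the CSR, state which rule was applied to the 4 Part 2 subjects. The by-subject listing in SAP 4.1 gives reasons for stopping drug or study, but not the rule behind them.

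The cost is a wording edit and one sentence, with no new data or visits. The downside is that some viremic subjects without new resistance stay on study drug with a retest in 1 to 3 weeks, which 6.10.1 B already allows. Since the study has stopped, only the CSR sentence still has effect here; the 3.3 edit matters if the text is reused.
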